7.12 Pharmacodynamic EBNA1 inhibition

No TLF's will be provided for abbreviated CSR as no biopsies were collected.

7.13 Efficacy

The number and percentage of patients for best overall response (BOR) will be provided. The number and percentage of patients with ORR will also be summarized together with exact 95% confidence intervals (CI) using a binomial distribution for Response Evaluable Population.

The endpoint objective response rate (ORR) is defined as the number and percentage of patients whose best overall response is either a complete response (CR) or partial response (PR). To qualify as a responder, a patient must have a complete or partial visit response confirmed by a second scan performed at least 4 weeks after the criteria for response are first met. A by subject listing will also be provided for Overall Response.

7.14 Safety

Safety objectives in this study will be assessed using the following endpoints in the All Treated population:

- Incidence of adverse events, SAEs, adverse events meeting protocol-defined DLT criteria, severe adverse events, adverse events leading to study treatment or study discontinuation, and adverse events resulting in death.
- Incidence of clinical laboratory test abnormalities including hematology and serum chemistry abnormalities assessed at protocol designated time points
- Changes in vital signs relative to baseline include blood pressure and heart rate measured at protocol designated time points

7.14.1 Adverse Events

Adverse events will be listed, including the verbatim description and MedDRA preferred term and system organ class (SOC).

Treatment emergent adverse events (TEAEs) are defined as those starts or severity becomes worse after the first dose of study treatment.

TEAE leading to study treatment discontinuation and death will be summarized by SOC, by preferred term and by maximum CTCAE grade (according to NCI CTCAE Version 5.0). The incidence of TEAEs will be based on the numbers and percentages of patients with events and number of events. In addition summary of DLT will also be provided for first cycle.

TEAE data will be presented across all cycles and for each cycle. The denominator for each cycle will be the number of patients available at the start of the cycle who received at least 1 dose of study drug for that cycle.

Individual patient listings will be prepared for AE leading to study treatment discontinuation and death. Listing of the first cycle DLTs for each cohort will be provided.

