## **Adverse Events**

All adverse events will be listed, including the verbatim description and MedDRA preferred term and system organ class (SOC).

Treatment emergent adverse events (TEAEs) are defined as those occurring after the first dose of study treatment.

TEAEs will be summarized by SOC and by preferred term. The incidence of TEAEs will be based on the numbers and percentages of patients with events and number of events. TEAEs will be further summarized by severity (according to NCI CTCAE Version 5.0) and relationship to study treatment.

An overall summary of adverse event incidence will also be presented by dose level to include the number and percentage of patients with at least one: TEAE, treatment related TEAE, Grade 3 to Grade 5 TEAE, death, SAE, treatment related SAE, DLT, TEAE leading to study treatment discontinuation, TEAE leading to dose modifications (e.g. dose reduction) and TEAE leading to study discontinuation.

TEAE data will be presented across all cycles and for each cycle. The denominator for each cycle will be the number of patients available at the start of the cycle who received at least 1 dose of study drug for that cycle.

Individual patient listings will be prepared for all AE data. Listing of the first cycle DLTs for each cohort within each phase will be provided.

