4 ENDPOINTS

4.1 **Primary Endpoints**

Phase 1:

• The frequency, severity, and duration of AEs and DLTs, AEs leading to discontinuation. and AEs leading to death.

Phase 2a:

• The durable ORR rate as well as ORR, DOR, DCR-6, DCR-12, PFS, rate of survival, and OS per RECIST v1.1.

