4.2 Secondary Endpoints

Phase 1:

- The rate and severity of treatment emergent AEs at the MTD and BCAD.
- Single dose and steady state plasma pharmacokinetic parameters of VK 2019.
- Incidence of safety laboratory assessment abnormalities
- Incidence of abnormalities in vital signs or other clinical safety assessments
- ORR, DOR, and Disease control rate (DCR) per RECIST v1.1
- Rate of partial or complete plasma EBV DNA antiviral response during treatment (assessed as 3xlog¹⁰ reduction or a drop below the lower limit of detection of the assay [LLOD], respectively).

Phase 2a:

- The rate and severity of treatment emergent AEs at the MTD, BCAD, and RP2D.
- Rate of partial or complete plasma EBV DNA antiviral response during treatment (assessed as 3xlog¹⁰ reduction or a drop below the lower limit of detection of the assay [LLOD], respectively).
- Plasma PK parameters of VK-2019.

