7.4 Subject Accountability

Summaries of analysis populations and subject disposition will be presented by cohort and will contain the following information:

- Number of subjects enrolled
- Number and percent of subjects who were dosed
- Number and percent of subjects who discontinued early from the study and reason for early discontinuation
- Number and percent of subjects who discontinued treatment and reason for discontinuation
- Number and percent of subjects in the All Treated Population, Response Evaluable Population and EBV DNA Population
- Number and percent of subjects entered in safety and long term follow-up

This table will be based on All Enrolled Population.

Subject disposition listing will be provided for All Enrolled Population.

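### SAP 7.14.1 specifies only part of the adverse-event summaries that the retained Phase 1 endpoints need; the DLT denominator and the AE partial-date rule need smaller corrections

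*SAP*

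**What the plan says.** **Endpoints.** SAP 4.1 keeps as the Phase 1 primary endpoint "The frequency, severity, and duration of AEs and DLTs, AEs leading to discontinuation. and AEs leading to death". SAP 4.2 keeps as a Phase 1 secondary endpoint "The rate and severity of treatment emergent AEs at the MTD and BCAD". SAP 7.14 names the incidence of AEs, SAEs, DLTs, severe AEs, AEs leading to treatment or study discontinuation, and fatal AEs, all in the All Treated population.

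**Outputs in the SAP.** Section 7.14.1 provides an AE listing with verbatim term, preferred term and SOC. Its one table by SOC, preferred term and grade is restricted: "TEAE leading to study treatment discontinuation and death will be summarized by SOC, by preferred term and by maximum CTCAE grade". For TEAEs in general it gives a counting rule (patients, percentages, events) and says "TEAE data will be presented across all cycles and for each cycle". For DLTs there is a first-cycle summary, and "Listing of the first cycle DLTs for each cohort will be provided".

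**Outputs in the protocol.** Section 14.5.1 plans a summary of all TEAEs by SOC and preferred term. It adds: "TEAEs will be further summarized by severity (according to NCI CTCAE Version 5.0) and relationship to study treatment". It also plans a ten-item overview: "An overall summary of adverse event incidence will also be presented by dose level to include the number and percentage of patients".

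**DLT population.** Protocol 14.5.1 and SAP 7.14 both place DLT incidence on All Treated. SAP 2.2.1 (cohort completion) and the protocol's definition of the MTD count evaluable patients. SAP 7.3 lists no DLT-evaluable set.

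**Partial dates.** SAP 7.2.1 imputes a partial AE start to the first of the month, or to 1 January. If that falls before first dose it substitutes the first dose date, limited only by the stop date.

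**The concern.** Protocol section 14 plans no confirmatory inference, so in Phase 1 the descriptive safety tables are the primary analysis. A programmer who followed SAP 7.14.1 literally would have no instruction to tabulate the grade of TEAEs in general, how long AEs lasted, their relationship to VK-2019, or how TEAE rates differ by dose. For a dose-escalation trial whose first objectives are the MTD, the RP2D and the safety profile, the by-dose view is the most useful one.

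The other two rules are small. One can make a descriptive Cycle 1 DLT rate look lower than the rate among the patients on whom the MTD is judged. The other gives a false onset date to some AEs already known to have begun before dosing.

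**Working it through.** **1. Endpoints against outputs.** The documents give no figure to reproduce here; the check sets sections side by side.

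| Needed for | SAP 7.14.1 | Protocol 14.5.1 |
|---|---|---|
| AE severity (SAP 4.1) | Maximum grade only for TEAEs leading to treatment discontinuation or death | All TEAEs by severity |
| AE duration (SAP 4.1) | None | None |
| TEAE rate and severity at MTD/BCAD (SAP 4.2) | None | No MTD/BCAD table; overview by dose level |
| SAE and severe-AE incidence (SAP 7.14) | No table | In the by-dose overview |
| Relationship (protocol analysis section) | None | All TEAEs by relationship |

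The protocol's ten overview items sort as follows:

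- Covered in SAP 7.14.1 (4): any TEAE, TEAE leading to treatment discontinuation, death, DLT.
- Named only as endpoints in SAP 7.14 (3): SAE, Grade 3 to 5 TEAE (matched to severe AE), study discontinuation.
- Absent from SAP section 7 (3): related TEAE, related SAE, TEAE leading to dose modification.

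4 + 3 + 3 = 10. None has a by-dose summary specified in 7.14.1; one (DLT) has a by-cohort listing. The SAP does state cohort layout where it wants it: in 7.4, "Summaries of analysis populations and subject disposition will be presented by cohort".

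**2. DLT denominator.** Under SAP 2.2.1 a patient is evaluable after 75% of Cycle 1 doses, or after at least one dose and a Cycle 1 DLT. Every patient with a Cycle 1 DLT is therefore evaluable. A treated non-evaluable patient adds to the denominator and never to the numerator:

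rate = DLTs / (evaluable + treated non-evaluable)

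The number of treated non-evaluable patients is an assumption:

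- 0: 1/6 = 16.7%
- 1: 1/7 = 14.3%
- 2: 1/8 = 12.5%

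This holds for Cycle 1 DLTs only. Protocol section 6.3 lets the SRC declare a DLT outside the defined timing.

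**3. Partial dates.** Assumed first dose 10 October 2019, with the rule applied literally:

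| Recorded start | Stop | Date assigned by SAP 7.2.1 |
|---|---|---|
| September 2019 | ongoing | 10 October 2019 |
| September 2019 | 15 October 2019 | 10 October 2019 |
| September 2019 | 25 September 2019 | 25 September 2019 |
| 2018 | ongoing | 10 October 2019 |
| October 2019 | ongoing | 10 October 2019 |

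The last row is reasonable, because onset could have followed dosing. Rows one, two and four are wrong: the recorded month or year already places onset before dosing. Such records can exist because AEs are collected from consent (protocol section 13, Reporting Period). SAP 7.2.2 makes no such move for medication dates. SAP 7.14.1 defines a TEAE as starting or worsening after the first dose and does not class onset on the first dose date itself.

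**The case against.** The strongest reply is scope. SAP section 1 limits the plan to an abbreviated CSR. Its explicit statements of omission (7.5, 7.12, 7.14.6, 7.14.7, 7.15) appear where a whole topic is dropped. Where a topic is only reduced (7.6, 7.10, 7.11, 7.13, 7.14.2) the SAP is silent; the laboratory shift tables planned in the protocol, for example, disappear without comment. Silence in 7.14.1 fits that pattern and may be deliberate. This stands as far as intent goes: neither oversight nor decision can be inferred. It does not remove the mismatch, because sections 4.1, 4.2 and 7.14 keep the endpoints.

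A reader might infer that SAEs and severity are dropped altogether. The documents do not support that. SAP 7.14 commits to SAE and severe-AE incidence, and 7.14.1 has a listing and a general TEAE incidence rule. What is missing is a specified table. SAP 7.4 also tabulates treatment and study discontinuation with reasons by cohort, which gives related by-dose information, though not TEAE tables.

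A reader might also treat the duration gap and the All Treated DLT population as SAP departures. Both are inherited from protocol 14.5.1. Nor do the documents say whether an MTD or BCAD was declared; if none was, that particular summary has no content.

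On dates, the rule leans towards counting events as treatment-emergent and is limited by the stop date. Whether a re-dated AE becomes a TEAE is undetermined until first-dose-day onset is classed. The false onset date remains in either case.

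**Conclusion.** The point holds. Followed as written, SAP 7.14.1 leaves the Phase 1 primary endpoint only partly reported: severity of TEAEs in general, AE duration and TEAE rates by dose or at the MTD/BCAD have no specified summary, and SAE incidence is promised without a table. Six of the ten protocol overview items have no output in 7.14.1. This should be fixed.

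The DLT denominator is minor. Its effect is zero if every treated patient is evaluable; the 14.3% and 12.5% rest on assumed counts. It would be tempting to say that it could bias the MTD, but cohort completion and the MTD already count evaluable patients. The synopsis hypothesis of less than 18% with a DLT has no planned test attached.

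The partial-date rule is also minor, but it is wrong as written whenever the known month or year precedes first dose and the AE is unresolved at first dose. How often this occurs is unknown.

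Escalation and MTD decisions are not affected, and no inferential test depends on these outputs.

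**What to change.** 1. In SAP 7.14.1, restore the protocol 14.5.1 tables: all TEAEs by SOC and preferred term, by maximum grade and by relationship, plus the by-dose-level overview with all ten items including SAEs. Any declared MTD or BCAD can be identified in the by-dose output. Add a simple summary of AE duration. If the abbreviated CSR intentionally omits any of these, say so, and say that the endpoint is then only partly reported.
2. For dose-escalation patients, report the Cycle 1 DLT rate among those evaluable under SAP 2.2.1, with the number treated but non-evaluable. Report expansion-cohort DLTs separately with their own stated denominator (the same evaluability rule, or All Treated), so that these Phase 1 patients are not left without a rate. List separately any DLT that the SRC declares outside Cycle 1. Keep All Treated for other AEs.
3. In SAP 7.2.1, substitute the first dose date only when the known month and year match those of first dose, or the year alone if the month is missing. Otherwise keep the imputed pre-dose date. State in 7.14.1 how onset on the first dose date is classed.

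The cost is SAP wording and standard tables from data already collected. The downsides are a somewhat longer output list for an abbreviated report and, possibly, a slightly higher reported DLT rate.

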## **Dose-limiting Toxicity**

DLTs will be determined based on the incidence and intensity of AEs assessed as being at least possibly related to VK-2019 and occurring up to 28 days after initiation of QD VK-2019 dosing on C1D0.

- 6.3.1 Dose-limiting Hematologic Toxicity
  - Grade 4 neutropenia > 7 days
  - Grade 4 thrombocytopenia or Grade 3 thrombocytopenia associated with bleeding or requiring platelet transfusion
  - Grade 3 febrile neutropenia
  - Grade 4 anemia or anemia that requires blood transfusion
- 6.3.2 Dose-limiting Non-hematologic Toxicities

- Any Grade 3 or higher non-hematology toxicity, excluding the following:
  - Toxicities assessed by Investigator as clearly related only to disease progression or intercurrent illness
  - Elevations of AST, ALT, and bilirubin, that correct to Grade 1 within one week and do not meet any of the definitions of acute liver injury as listed below
  - o Other asymptomatic laboratory abnormalities
  - Grade 3 fever without neutropenia that returns to Grade 1 or less within 3 days, and is not associated with hemodynamic compromise (including hypotension, or clinical or laboratory evidence of end organ perfusion impairment)
  - Grade 3 diarrhea, nausea, vomiting, or abdominal pain that returns to Grade 1 or baseline within 3 days and with medical intervention
  - Grade 3 pruritis or rash that returns to Grade 1 or baseline within 7 days or baseline with medical intervention
  - o Grade 3 fatigue
  - Grade 3 tumor flare (defined as pain, irritation or rash that localizes to sites of known or suspected tumor)

A DLT will also include:

- A laboratory finding of acute liver injury defined as:
  - Sustained (> 1 week) doubling of AST or ALT levels to no less than 4 x ULN, or sign of increasing functional liver impairment with > 2x baseline increase in total bilirubin
  - o Increased AST or ALT levels above 8xULN
  - Suspected acute liver injury (per Hy's law) ALT/AST > 3 x ULN in combination with Total Bilirubin > 2 x ULN in the absence of cholestatic injury (ALP < 2 x ULN) and no other cause identified.

- Any AE resulting in a patient missing < 7 days of dosing with VK-2019
- Any AE not otherwise meeting the criteria or timing of a DLT as defined above, but is declared a DLT by the SRC

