#### **Definition of the MTD**

The MTD is defined as the highest dose level of VK-2019 at which fewer than two DLTs are observed in six evaluable dose escalation patients at that dose level.

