2.2.1 Definition of a Completed Cohort and an Evaluable Patient

Each dose escalation cohort will consist of either:

- 1 evaluable patient (Accelerated Titration cohorts), or
- 3-6 evaluable patients (Rolling Six cohorts)

To be considered evaluable, a patient will have and one of the following:

[figure not shown]
- Received 75% of doses during Cycle 1, or,
- Received at least one dose of VK-2019 and experienced a DLT during Cycle 1

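### The SAP's DLT summary and listing cover only the first cycle, so a DLT that the SRC declares later would be missing from the reported count.

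*SAP*

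**What the plan says.** **DLT definition.** The protocol section on dose-limiting toxicity starts from related events "occurring up to 28 days after initiation of QD VK-2019 dosing on C1D0". Its closing list (6.3.2) then adds a further category: "Any AE not otherwise meeting the criteria or timing of a DLT as defined above, but is declared a DLT by the SRC". The synopsis has the same category.

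**MTD rules.** The MTD is the highest dose at which "fewer than two DLTs are observed in six evaluable dose escalation patients at that dose level". Protocol 6.2.3 and SAP 2.2.3 treat the MTD as exceeded once two or more patients have a DLT. Neither rule mentions a cycle.

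**Evaluability.** Protocol 6.2.1 and SAP 2.2.1 give two routes. One is having taken 75% of Cycle 1 doses. The other is "Received at least one dose of VK-2019 and experienced a DLT during Cycle 1".

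**Reporting in the protocol.** Section 14.5.1 asks for an overall AE summary by dose level, in which DLT is one row with no cycle limit. It also says: "Listing of the first cycle DLTs for each cohort within each phase will be provided".

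**Reporting in the SAP.** Section 7.14 names the incidence of "adverse events meeting protocol-defined DLT criteria" in the All Treated population, again with no cycle limit. The outputs in 7.14.1 are narrower. The summary is described by "In addition summary of DLT will also be provided for first cycle" and the listing by "Listing of the first cycle DLTs for each cohort will be provided".

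**The concern.** The frequency of DLTs belongs to the Phase 1 primary endpoint (protocol 14.1.1, SAP 4.1), and defining the MTD is a Phase 1 primary objective. The protocol expressly allows for a DLT that misses the standard timing. Neither DLT output in SAP 7.14.1 can show one.

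A programmer who follows the SAP exactly would therefore produce a DLT table that is complete for Cycle 1 and silent about anything the SRC declared later. A reader of the report who sets that table beside the stated MTD could not reconstruct the MTD and might think that the two conflict. The SAP is also at odds with itself, because 7.14 states the DLT endpoint without a cycle limit and no output in 7.14.1 delivers it.

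**Working it through.** This is a question of counting rules, so the plan has no figure to reproduce.

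**Step 1. Set the rules side by side.**

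| Place | What is counted | Cycle limit |
|---|---|---|
| Protocol, DLT section, standard criteria | Related AEs meeting the criteria | 28 days from C1D0 |
| Protocol 6.3.2, SRC clause | Any AE the SRC declares a DLT | None |
| Protocol, MTD definition; 6.2.3 | DLTs in evaluable escalation patients | None stated |
| Protocol 14.5.1, overall AE summary | Patients with a DLT, by dose level | None stated |
| Protocol 14.5.1, listing | DLTs by cohort | First cycle |
| SAP 7.14, endpoint statement | AEs meeting DLT criteria, All Treated | None stated |
| SAP 7.14.1, summary and listing | DLTs | First cycle |

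The listing limit comes from the protocol. What the SAP adds is a first-cycle summary where the protocol has a row without a limit.

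**Step 2. Can a late DLT enter the MTD count?** Yes. A patient who took 75% of Cycle 1 doses is evaluable whatever happens later. If the SRC then declares a Cycle 2 event a DLT, that patient is an evaluable escalation patient with a DLT under the protocol's own definition.

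**Step 3. Example.** Take six treated patients at one dose, all evaluable, so that the All Treated and evaluable denominators agree. One has a Cycle 1 DLT. Another has a Cycle 2 event that the SRC declares a DLT.

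- SAP 7.14.1 summary: 1/6 = 16.7%. This fits the MTD definition and lies below the 18% in the Phase 1 hypothesis of the synopsis.
- Protocol definition: 2/6 = 33.3%. Read literally, the MTD is exceeded.

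**Step 4. How often could the two counts fall on opposite sides of the boundary?** The documents give no rate of late DLTs, so this step rests on assumptions. Let p be the probability of a Cycle 1 DLT. Let q be the probability of a late SRC-declared DLT in a patient without a Cycle 1 DLT. Patients are taken as independent. For a cohort of six, the probability of at most one patient with a DLT in the first-cycle table but at least two overall is

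P = P(X = 0) × P(Bin(6, q) ≥ 2) + P(X = 1) × P(Bin(5, q) ≥ 1), with X ~ Bin(6, p).

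For p = 0.10 and q = 0.05: 0.5314 × 0.0328 + 0.3543 × 0.2262 = 0.0174 + 0.0801 = 0.0976 (summed before rounding).

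| p | q = 0.02 | q = 0.05 | q = 0.10 |
|---|---|---|---|
| 0.05 | 0.0265 | 0.0766 | 0.1791 |
| 0.10 | 0.0371 | 0.0976 | 0.2058 |
| 0.17 | 0.0405 | 0.1016 | 0.2019 |

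Over this assumed range the probability runs from about 3% to 21% per six-patient cohort.

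**The case against.** **The protocol already asks for the missing summary.** This is correct. The overall AE summary in 14.5.1 has a DLT row without a cycle limit, so a claim that every DLT output in both documents omits late DLTs would be wrong. The gap lies in the SAP, which leaves that row out. The SAP serves an abbreviated report, and that may explain the omission, but the item dropped concerns a primary endpoint.

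**The SRC sets the MTD, not this table.** Also correct. A reader might infer that one late event would reverse the MTD conclusion. The documents do not support that. Under protocol 6.1.1 and 6.2.3 the SRC decides when a cohort is complete, its decisions are documented, and nothing in the SAP derives the MTD from the 7.14.1 table. The documents also do not say whether a DLT declared after a cohort has been reviewed reopens its count, so 2/6 as an exceeded MTD is the literal reading and not a stated consequence.

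**The evaluability wording.** A reader might infer that a patient with under 75% of Cycle 1 doses and a late SRC-declared DLT drops out of both numerator and denominator. That fails for the SAP's reporting, which uses the All Treated population. The wording bears only on cohort completion and the MTD count, and the case is narrow. Fewer than 75% of 28 daily doses means that more than 7 were missed, and the synopsis makes an AE that causes more than 7 missed days a DLT in its own right. Section 6.3.2 prints fewer than 7 days at the same place, and the two must be reconciled.

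**A late DLT is not hidden.** Protocol section Patient Withdrawal makes a DLT a reason to stop treatment, and SAP 7.14.1 summarizes and lists TEAEs leading to discontinuation. It also presents TEAE data across all cycles. So the event could well appear, but no output is specified that would identify it as a DLT.

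**The harm is conditional.** It needs a late declaration by the SRC, and it matters most at the boundary between one and two DLTs. This stands, and it limits the severity.

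**Conclusion.** The point holds as a reporting defect that should be fixed. The DLT outputs in SAP 7.14.1 are narrower than the protocol's DLT definition, its MTD rules, its summary by dose level and the SAP's own endpoint statement in 7.14. If the SRC declares a late DLT in an evaluable escalation patient, the reported count is too low by that event and may seem inconsistent with the stated MTD. In a six-patient cohort at the boundary, this is 1/6 shown against 2/6 under the protocol definition.

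The conclusion depends on a late declaration being made. SRC-declared DLTs within Cycle 1 are captured as the SAP stands. The 3% to 21% range illustrates assumed rates and is not an estimate for this drug. No dose decision changes.

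**What to change.** In SAP 7.14.1, replace the first-cycle summary and listing with a summary and listing of all protocol-defined DLTs by dose level, including those declared by the SRC. Show cycle of onset, flag SRC-declared events and keep the first-cycle DLTs as a marked subset. Because 7.14 uses the All Treated population and the MTD definition uses evaluable dose escalation patients, show the count in the latter group as well. Amend the listing sentence in protocol 14.5.1 to match. If no late DLT was declared, one sentence in the report saying so settles the matter.

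Separately, the sponsor should reconcile the Cycle 1 wording of the evaluability rule (protocol 6.2.1, SAP 2.2.1) with the SRC clause in 6.3.2, and the two versions of the missed-dose criterion in the synopsis and 6.3.2. No clinical rule is proposed here.

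The cost is a few lines of text, an onset-cycle variable and one flag in the AE dataset. The downside is that the displayed DLT count may be higher.
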